5.6.2 Subject Disposition

The number of subjects included in each analysis population (FAS, Safety, PP) will be summarized, as well as the reasons for exclusion from each population. The number of subjects enrolled, completed, and discontinued (including the reasons for discontinuation) will be summarized.

5.6.3 Demographic and Baseline Characteristics

Subject demographic and baseline characteristics will be summarized descriptively for the FAS, PP and safety populations. Demographic variables will include variables such as age, race, ethnicity, height, and weight. Baseline characteristics will include variables such as pre-treatment MBL, fibroid volume and uterine volume.

5.6.4 Efficacy Analyses

Efficacy evaluations will be summarized descriptively, by visit.

5.6.4.1 Primary Efficacy Analysis

Table 3 describes the two co-primary endpoints. Each subject will be determined to be a Success or Failure per the subject success criteria. For the endpoint of Reduction in Menstrual Blood Loss, the count and percentage of subjects with Success and Failure will be summarized, along with the 95% exact confidence interval for the percent successes. The rate of surgical reintervention during 12 months, along with 95% confidence interval, will be determined using Life-Table methods. Each endpoint has a pre-specified study success criterion, as described in Table 3. Study success is achieved if both of study success criteria are met.

Table 3: Co-Primary Endpoints and Success Criteria

Co-Primary Endpoint	Test Method	Subject Success Criteria ^a	Study Success Criteria
Reduction in MBL at 12 months	Modified pictorial blood loss assessment chart (PBAC)	≥ 50% reduction in PBAC score, and a final PBAC score < 250	LCL of the percentage of subject success ≥ 45%
Rate of surgical reintervention for HMB due to treatment failure at 12 months	Surgical reintervention for HMB due to treatment failure	No surgical reintervention for HMB due to treatment failure at 12 months	LCL of the percentage of subject success ≥ 75%

^a Subject success is calculated separately for the two co-primary endpoints, such that it is possible for a subject to be considered a success for one co-primary endpoint and not for the other.

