5.5 Efficacy and Safety Variables

5.5.1 Co-Primary Efficacy Variables

5.5.1.1 Pictorial Blood Loss Assessment Chart (PBAC)

Subjects will be asked to assess menstrual bleeding using a PBAC menstrual diary. The PBAC is a visual representation of blood loss from which a numerical score is derived. The PBAC is detailed in Appendix D. PBAC scoring instructions are included in Appendix E.

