5.6 Statistical Methods

All statistical processing will be performed using SAS® unless otherwise stated.

Continuous variables will be summarized descriptively using number of subjects (n), mean, standard deviation (SD), minimum, median, and maximum. Categorical variables will be summarized descriptively using frequency counts and percentages.

Analyses presented for the Full Analysis Set¹ (FAS) will be considered primary. Analyses performed on the Per-Protocol (PP) will be secondary and supportive.

¹ International Conference on Harmonization (ICH) – E9 Statistical Principles for Clinical Trials

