5.6.1 Analysis Populations

The FAS population will be comprised of all study subjects who were treated and who do not meet any of the following criteria:

- Become pregnant during the 12-month post-procedure study period;
- Are diagnosed with a medical condition that would make assessment of menstrual bleeding invalid or unreliable.

The safety population will be comprised of subjects who were treated and have post-baseline information.

The per-protocol (PP) population will include subjects who complete 12 months of follow-up without study protocol violations. The PP population will include subjects from the FAS population who do not meet any of the following criteria:

- Violated the inclusion/exclusion criteria;
- Did not complete a 12 month PBAC;
- Are associated with protocol violations that are considered to influence the endpoint under evaluation;

Subjects who discontinue the study due to a device/procedure-related adverse event (AE) or documented lack of efficacy (without surgical reintervention) will be included in the PP population, with missing data imputed as failure for the 12-month menstrual blood loss (MBL) endpoint.

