5.6.8.2 Handling of Dropouts or Missing Data

Reduction in MBL at 12 Months

Missing 12-month menstrual blood loss data will be imputed using last observation carried forward (LOCF). Subjects which undergo surgical reintervention to manage fibroid symptoms prior to 12 months will be excluded from the Reduction in Menstrual Blood Loss analysis.

Surgical Reintervention for HMB due to Treatment Failure at 12 Months

Life-Table methods will be used to calculate the success rate and 95% confidence interval for the rate of surgical reintervention during 12 months. Therefore, subjects that are discontinued prior to 12 months for reasons other than surgical reintervention will be considered censored.

Sensitivity Analyses

Sensitivity analyses will also be conducted to examine the impact of missing data. A worst-case analysis (all missing data imputed as failures) and best-case analysis (all missing data imputed as successes) will be performed. In addition, a tipping point analysis will be performed.

Secondary Endpoint Analyses

No imputations will be made for missing secondary endpoint data.

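### A woman whose PBAC falls on bleeding medication started after treatment counts as a device success, and no planned FAS analysis would show it

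*SAP*

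**What the plan says.** SAP 5.6.4.1, Table 3, sets the subject criterion for MBL at 12 months as "≥ 50% reduction in PBAC score, and a final PBAC score < 250"; Protocol Table 1 (9.1) has the same criterion. The study criterion is a lower confidence limit of at least 45%, from a 95% exact interval.

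The FAS is the primary set. Under SAP 5.6.1 a treated woman leaves it only for pregnancy or under the criterion "Are diagnosed with a medical condition that would make assessment of menstrual bleeding invalid or unreliable". SAP 5.6.8.2 carries the last observation forward when the 12-month value is missing. The only post-treatment event it gives an MBL rule is surgical reintervention. It then states: "Sensitivity analyses will also be conducted to examine the impact of missing data".

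The per-protocol (PP) set drops women who "Are associated with protocol violations that are considered to influence the endpoint under evaluation". Of women who discontinue, it says that those with "documented lack of efficacy (without surgical reintervention) will be included in the PP population, with missing data imputed as failure" for MBL. SAP 5.6 adds: "Analyses performed on the Per-Protocol (PP) will be secondary and supportive".

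Protocol 12.3 has sites ask about medication taken for heavy bleeding at every visit through 12 months. Protocol 19.4 leaves further analysis detail to the SAP. The SAP's subgroups (5.6.8.6) do not involve medication, and its table index (Section 6) lists no concomitant-medication table.

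**The concern.** A woman whose bleeding is not adequately controlled after ablation may start or increase a drug to reduce it. If her PBAC on that drug is at least halved and below 250, she is a primary success. The trial has no comparator arm to absorb the drug effect, so the fall is attributed to the device. Because such a drug is taken to reduce bleeding, the expected bias is toward success. The information needed to identify these women is collected but has no stated use in any FAS efficacy or sensitivity analysis.

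**Working it through.** **Does any stated rule reach her?** Take a treated woman who starts an HMB drug at month 8, stays in the study and returns a qualifying 12-month PBAC.

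- *Endpoint (SAP Table 3):* PBAC only, so she is a success.
- *FAS (SAP 5.6.1):* she is neither pregnant nor newly diagnosed with a condition, so she stays in.
- *Sensitivity analyses (SAP 5.6.8.2):* her value is observed, so all three leave it unchanged.
- *PP (SAP 5.6.1):* she is removed only if the drug is judged a violation that influences the endpoint. Removal takes her out of the denominator; it does not make her a failure. The PP failure imputation covers missing data after discontinuation, and she has neither.
- *Is it a violation?* Inclusion 8 (Protocol 4L) covers non-injectable hormonal contraception. Exclusion 32 restricts antifibrinolytics only during screening, so starting one later is not clearly a violation.

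**Reproducing the plan's sample size.** Inputs from SAP 5.6.7 and Protocol 19.1: threshold 0.45, assumed success 0.60, two-sided 95% exact interval, n = 125; 147 women are to be treated.

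- Lower limit for x successes in n: LCL = the 0.025 quantile of Beta(x, n − x + 1).
- Critical count c = smallest x with LCL ≥ 0.45. For n = 125, c = 68 (LCL 0.4525; 67 gives 0.4446). For n = 147, c = 79 (LCL 0.4534; 78 gives 0.4466).
- Power = P(X ≥ c) at p = 0.60: 0.914 for n = 125 and 0.948 for n = 147. The SAP's 125 for 90% power is reproduced.

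**How many reclassified successes reverse the result?** The count is observed successes − c + 1. Observed rates and denominators are assumptions.

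| Observed rate | Successes (LCL), n = 125 | Reversal count | Successes (LCL), n = 147 | Reversal count |
|---|---|---|---|---|
| 55% | 69 (0.4605) | 69 − 68 + 1 = 2 (1.6%) | 81 (0.4669) | 81 − 79 + 1 = 3 (2.0%) |
| 60% | 75 (0.5086) | 75 − 68 + 1 = 8 (6.4%) | 88 (0.5147) | 88 − 79 + 1 = 10 (6.8%) |
| 65% | 81 (0.5575) | 81 − 68 + 1 = 14 (11.2%) | 96 (0.5702) | 96 − 79 + 1 = 18 (12.2%) |

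At 60%, the criterion survives 7 reclassifications of 125 (5.6%) or 9 of 147 (6.1%).

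**The same point as false-positive risk, n = 125.** Suppose success without medication is exactly 45% and on-drug successes add m to the observed rate. The chance of passing is 2.2% at m = 0, 5.9% at m = 2 points, 18.6% at 5 points and 59.0% at 10 points.

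**The case against.** *The rule may exist elsewhere.* The SAP says "PBAC scoring instructions are included in Appendix E", and SAP Appendices D and E and Protocol Appendices F, G and H were not available. This stands as a limit: the absence is established only for the text at hand.

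*The protocol has safeguards.* Inclusion 8 asks for uniform use or non-use of non-injectable hormonal contraception through 12 months, and its footnote has the sponsor supply the oral contraceptive if insurance would force a change. Protocol 10.5 has adherence checked at follow-up, 10.6 allows removal for non-adherence, and 17.1 and 17.3 have deviations graded by the sponsor with Medical Advisory Board review. Changed contraception could therefore be a major deviation that PP removes. This narrows the gap, mainly to antifibrinolytics and other drugs outside the contraception commitment. It does not close it: these provisions feed the supportive PP set or create missing data, and neither touches an observed on-drug PBAC in the FAS.

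*Analysing PBAC regardless of medication is a legitimate treatment-policy choice.* It is, so the proposal leaves the primary analysis alone. But the choice is not stated, and nothing planned shows how much the result depends on it.

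*Materiality is assumed.* Correct. At 60%, reversal needs about 11% of all successes to be on such medication (8/75 = 10.7%; 10/88 = 11.4%). The 55% row lies below the design assumption and only one or two successes above the critical count, where almost any reclassification would matter.

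*HMB medication is undefined.* Fair; the fix has to define it.

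**Conclusion.** The concern holds on the supplied text. MBL success depends on PBAC alone, the FAS keeps women on newly started or increased HMB medication, and the planned sensitivity analyses cannot reach them when the 12-month PBAC is observed. The expected direction favours the device. The size cannot be estimated because no rate of such use is given; the 8 of 125 and 10 of 147 figures assume an observed 60% and that every such woman would otherwise have failed. Confidence is medium because of the unavailable appendices. This should be corrected in the SAP; it does not make the primary analysis or the sample size wrong.

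**What to change.** Add one pre-specified FAS sensitivity analysis of MBL to SAP 5.6.8.2. A woman counts as a failure if HMB medication was newly started or increased after treatment and was in use during the cycle of her 12-month PBAC, or of the PBAC carried forward. Contraception kept stable under Inclusion 8 does not count. Fix the coding before database lock: start from the bleeding indication that sites already record, and state how contraception changed for other reasons is handled. Report the number of MBL successes on such medication. If an appendix already holds a rule, cross-refer to it in 5.6.8.2. Surgical reintervention in the MBL analysis is a separate matter. The change affects analysis only, not who may receive medication.

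The cost is SAP wording, a coding step and one output, assuming the case report form (not supplied) records start and stop dates and dose changes. The supporting result may be less favourable, and some women who would have passed without the drug are classed as failures in it. Primary power is unchanged. If the sponsor chose to make this the primary rule, that would be an estimand decision with a price. Were 3% or 5% of subjects, within the assumed 60%, such successes, power would fall from 91.4% to 75.2% or 59.0% at n = 125, and from 94.8% to 81.1% or 65.2% at n = 147.

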5.6.4.2 Secondary Efficacy Analysis

There are six secondary endpoints:

- Change in total fibroid volume from Baseline to 12 months
- Change in perfused fibroid volume from Baseline to 12 months
- Change in UFS-QOL from Baseline to 12 months
- OTE at 12 months
- Subject satisfaction at 12 months
- Change in EQ-5D from Baseline to 12 months

Secondary endpoints will be summarized using descriptive statistics.

5.6.5 Procedure Summaries

The following procedure related information will be summarized using descriptive statistics:

- Subject pain and tolerance of procedure
- Time to return to daily activities
- LOS (start of procedure to discharge)

- Time from entry into procedure room to discharge
- Procedure time
- Device malfunctions
- Procedure location (site of service)
- Number of fibroids treated
- Size of fibroids treated
- Number of ablations per fibroid
- Anesthesia and procedure-related medications
- Pain medication and narcotic use during recovery

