9.2 SECONDARY ENDPOINTS

Table 2 provides a list of the secondary endpoints in the study and the method of measurement for each. The secondary endpoints are reached at 12 months.

Table 2 Secondary Endpoints

Secondary Endpoint	Test Method
Safety - Adverse Device Effects	Procedure safety will be assessed by recording all adverse device effects that occur during or subsequent to treatment on the day of the procedure. Longer-term safety will be assessed by recording at each follow-up visit any untoward medical occurrence since baseline. Each adverse device effect will be assessed for severity.
Reduction in total and perfused fibroid volumes	Change in total and perfused volume of clinically relevant fibroids will be determined by comparing contrast-enhanced MRI at baseline and at 12 months. All MRI's will be forwarded to a central reader (core lab).
Change in the symptom severity and quality of life subscales of the Uterine Fibroid Symptom and Quality of Life (UFS-QOL) Questionnaire	The Symptom Severity Score (SSS) and Health-Related Quality of Life Score (HRQL) are calculated from a subset of the Uterine Fibroid Symptom and Quality of Life (UFS-QOL) questionnaire, a validated and fibroid-specific assessment tool. ¹⁰ The questionnaire and the SSS component have been used in several studies of subjects with fibroids. A copy of the UFS-QOL questionnaire is included as Appendix B.
Time to return to normal daily activity (days)	Subjects will be given a Treatment Recovery Questionnaire at discharge and asked to complete questions daily regarding return to normal activities for the first two weeks post-procedure. A copy of the questionnaire is included as Appendix C.
Overall subject treatment outcome using the Overall Treatment Effect Scale (OTE)	Subject-perceived overall treatment effect (OTE) will be assessed using the OTE Scale. ¹¹ Subjects will be asked to indicate whether their uterine fibroid symptoms have improved, remained the same, or worsened. If the subject indicates that her symptoms have improved, she will be asked to rate the degree of improvement on a 7-point scale from "almost the same, hardly better at all" (1) to "a very great deal better" (7). If the subject indicates that her symptoms worsened, she will be asked to rate the degree of worsening on a 7-point scale from "almost the same, hardly worse at all" (-1) to "A very great deal worse" (-7). OTE is assessed as part of the Subject Satisfaction Questionnaire included as Appendix I.

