12.3 Follow-up Phase

- A. Follow-up visits will occur in accordance with Table 6 below. The day of the Sonata treatment represents Day 0. Study visits that do not occur within the below time windows will be considered protocol deviations.

Table 6 Follow-up (FU) Visit Windows

Visit	Allowed Visit Date Range
FU Visit 1 - 10 days	± 4 days
FU Visit 2 - 30 days	± 1 week
FU Visit 3 - 3 months	± 2 weeks
FU Visit 4 - 6 months	± 4 weeks
FU Visit 5 - 12 months	± 2 months
FU Visit 6 - 2 years	± 2 months
FU Visit 7 - 3 years	± 2 months

- B. The measurements and evaluations that will occur at each follow-up visit are provided below.

- 1) Follow-up Visit 1: 10 Days (± 4 days)
(Phone Call or visit at Investigator's discretion)

(a) Adverse Events

The primary purpose of Follow-up Visit #1 is to assess safety. Subjects will be asked if they have experienced any untoward medical occurrences since the Sonata treatment. If so, these events will be recorded on the Adverse Event case report form, in accordance with the procedures outlined later in this protocol.

(b) Post-treatment follow up

Subjects will be asked whether there is any change to their medical status. Subjects will be asked specifically if they have experienced any signs or symptoms of fibroid shedding: cramping, bleeding, passage of any tissue per vaginam.

(c) Concomitant Medications

Subjects will be asked about concomitant medications, noting in particular concomitant medications taken for the treatment of HMB.

(d) Adherence with/Continuance of Birth Control Method

Subjects will be asked if they are adhering to their chosen method of birth control, and if there have been any changes in their birth control method, including changes to medication type and preparation.

2) Follow-up Visit #2: 30 Days (\pm 1 week)

(a) Adverse Events

Subjects will be asked if they have experienced any untoward medical occurrences since the Sonata treatment. If so, these events will be recorded on the Adverse Event case report form, in accordance with the procedures outlined later in this protocol.

(b) Return to Normal Daily Activity

Subjects will be asked to submit their completed Treatment Recovery Questionnaire (Appendix C). Subjects who are not back to normal activity will be followed up by phone visits weekly until the subject has resumed normal activity or the reason for not resuming normal activity is not expected to change.

(c) Surgical Reintervention

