5.5.3.2 Treatment Recovery Questionnaire

Subjects will be given a Treatment Recovery Questionnaire at discharge and asked to complete questions daily regarding return to normal activities for the first two weeks post-procedure. A copy of the questionnaire is included as Appendix C.

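### Time to return to normal activity has no rule for women without a return date, so its mean and maximum, and slightly its median, lean toward faster recovery if any exist

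*SAP*

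**What the plan says.** Protocol 9.2 (Table 2) makes time to return to normal activity, in days, a secondary endpoint. The SAP treats it differently. SAP 5.6.4.2 says "There are six secondary endpoints" and this variable is not among them. It appears in SAP 5.6.5, under the sentence "The following procedure related information will be summarized using descriptive statistics", as "Time to return to daily activities". SAP 5.6 states what that means: "Continuous variables will be summarized descriptively using number of subjects (n), mean, standard deviation (SD), minimum, median, and maximum". The only listed output that fits is Table 14.2.4, the procedure summary in the full analysis set. No time-to-event table is listed for it.

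On data collection, women are "asked to complete questions daily regarding return to normal activities for the first two weeks post-procedure" (SAP 5.5.3.2) and hand in the form at the 30-day visit. Under Protocol 12.3 (30-day visit), those not yet back are telephoned weekly "until the subject has resumed normal activity or the reason for not resuming normal activity is not expected to change". The footnotes to Protocol Table 4 and SAP Table 2 repeat this stopping rule.

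On missing data, SAP 5.6.8.2 says "No imputations will be made for missing secondary endpoint data". Censoring is specified only for surgical reintervention.

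**The concern.** The variable is a time to an event, and the plan's own stopping rule lets follow-up end before the event. A woman closed in that way has no number of days to report, and neither has one who is lost before resuming. With no assigned value and no censoring, she can enter neither the mean, the median nor the maximum. The maximum becomes the slowest time among women who did return.

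For a woman who never resumes, the direction is certain: her time exceeds every day on which she was followed. Recovery time is a natural selling point for a minimally invasive procedure, and a single-arm study has no comparator group in which the same omission would occur. The plan does not ask for the number not resumed, so a reader of the results could not judge the effect.

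**Working it through.** **1. Is there anything to reproduce?** No. The documents state no expected recovery time, spread or non-return rate. The only trial figure used below is the 147 treated women (Protocol 19.1). Everything else is an assumption, used to show a range.

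**2. Effect on the mean.** Assume women who return average 5 days, *m* women never return, and those women are counted to a horizon *H*. The planned summary gives 5.0 days whatever *m* is. Counting everyone gives

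((147 − *m*) × 5 + *m* × *H*) / 147, an excess of (*m*/147) × (*H* − 5).

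| *m* of 147 | *H* = 60 days | *H* = 30 days |
|---|---|---|
| 3 (2%) | (144×5 + 3×60)/147 = 6.12 | (144×5 + 3×30)/147 = 5.51 |
| 7 (5%) | (140×5 + 7×60)/147 = 7.62 | (140×5 + 7×30)/147 = 6.19 |
| 15 (10%) | (132×5 + 15×60)/147 = 10.61 | (132×5 + 15×30)/147 = 7.55 |

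The result depends heavily on *H*, which is a choice.

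**3. Effect on the median.** If the *m* women rank last, the median of all 147 is the 0.5 × 147/(147 − *m*) quantile of the returners: 73.5/144 = 51.0%, 73.5/140 = 52.5% and 73.5/132 = 55.7%. The median therefore moves little.

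**4. Non-return and loss together.** The simulation used n = 147, 400 runs per setting and lognormal recovery times with log-SD 0.8. Loss was uniform over days 0 to 30 and unrelated to recovery; follow-up otherwise ran to day 60, and women who never resume stayed at risk. Times are in days.

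| Assumed median | Never resume | Lost | Women with a time | Mean: observed only | Mean: restricted to day 60 | Median: observed only | Median: Kaplan-Meier |
|---|---|---|---|---|---|---|---|
| 4 | 0% | 0% | 147 | 5.45 | 5.47 | 3.99 | 4.00 |
| 4 | 0% | 15% | 143 | 5.36 | 5.50 | 3.94 | 4.00 |
| 4 | 5% | 5% | 138 | 5.44 | 8.22 | 3.98 | 4.24 |
| 4 | 10% | 0% | 132 | 5.49 | 11.01 | 4.03 | 4.52 |
| 10 | 0% | 0% | 145 | 12.90 | 13.46 | 9.91 | 10.03 |
| 10 | 0% | 15% | 136 | 12.50 | 13.54 | 9.55 | 10.01 |
| 10 | 10% | 15% | 123 | 12.54 | 18.09 | 9.58 | 11.22 |

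In the 10-day setting with nobody lost, two women on average lack a time because their recovery runs past day 60.

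With no non-return and no loss in the 4-day setting, the two approaches agree. Loss alone has a small effect. Non-return drives the mean. The largest shift in the median is (11.22 − 9.58)/11.22 = 15%.

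**The case against.** The case on the other side is substantial.

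- **The no-imputation sentence.** It covers secondary endpoint data, and the SAP does not list this variable as a secondary endpoint. The sentence reaches it only through the protocol's classification. That is correct, but on the SAP's own list no missing-data rule covers the variable at all, and the gap is the same.
- **Exclusion is not written down.** It is inferred, and the SAP reports n, so a shortfall would show. The inference is nevertheless hard to avoid, because a mean of days needs a number of days. A bare n does not separate women who never resumed from women lost or with a missing form.
- **The stopping rule is a contingency.** A reader might infer that the protocol expects women who never recover. It only provides for them, and the weekly calls capture late returners who do return.
- **Women lost early need not be slow.** One lost in the first week may have recovered soon afterwards; her time is known only to exceed her last contact. A reader might infer that all omitted women are the slowest. The documents support that only for those who never resume.
- **The variable is descriptive.** It has no hypothesis or threshold and plays no part in study success. This stands and limits the weight of the point.

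**Conclusion.** The point holds as a gap in the planned analysis, worth correcting but without bearing on the co-primary endpoints. Women with no return date leave the summary. For those who never resume, the mean and maximum shift toward faster recovery, and the median shifts slightly. For those lost, the same direction follows if loss is unrelated to recovery speed, and the effect is small.

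The size is not known, because the documents give no non-return rate; with no non-returners and no loss the bias is zero. The median shifts by about 0% to 15% over the assumed settings.

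A reader might infer from the illustrations that the reported mean could be half the true one. The documents do not support that: the rates, recovery times and horizon are all assumed, and a restricted mean is reported neither by the SAP nor by the change proposed here.

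**What to change.** In SAP 5.6.5, summarise the variable by Kaplan-Meier in all treated women, with two separate rules:

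- Women lost to contact before resuming are censored at their last contact.
- Women whose calls were closed because no change was foreseen stay in the risk set as not recovered, to a horizon stated in advance. Censoring them at last contact would be informative: it would treat them as being as likely to return as women still being followed.

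Report the median with its 95% confidence interval, the proportions back by days 7, 14 and 30, and the numbers never resumed and lost. Add the corresponding output table. Classify the variable the same way in the protocol and the SAP.

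The cost is a few lines of SAP text and one extra run, with no new data collection. The SAP already uses life-table methods for reintervention. The reported recovery figure may become slightly less favourable.
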